5.5. Extent of Study Treatment Exposure and Compliance

Extent of treatment exposure will be summarized using descriptive statistics based on SAF for neoadjuvant and adjuvant treatment period, respectively.

5.5.1. Measurement of Compliance

Drug compliance records, including investigational drug vials dispensed and actual drug administration, will be provided.

5.5.2. Exposure to Investigational Product

Exposure to cemiplimab will be examined for each subject and the following variables will be summarized :

- The total number of doses administered
- The mean dosage administered (mg)
- Duration of treatment exposure (in weeks) calculated as the minimum of
 - [date of last dose – date of first dose + 21 days] /7
 - or
 - [date of clinical data cut-off or date of death - date of first dose + 1] /7

The number and percentage of subjects exposed to cemiplimab will be presented by specific time point of interest.

5.6. Analyses of Efficacy Variables

The analysis of efficacy data will be performed based on the FAS, as defined in Section 3.1.

5.6.1. Analysis of Primary Efficacy Variable

The pCR rate per independent central pathology review along with a two-sided 95% exact confidence interval (CI) will be calculated using Clopper-Pearson method (Clopper, 1934).

5.6.2. Analysis of Secondary Efficacy Variables

The pCR rate per local pathology review, mPR rate per independent central pathology review, mPR rate per local pathology review, and ORR prior to surgery per investigator assessment will be summarized and corresponding two-sided 95% exact CIs will be calculated by Clopper-Pearson method (Clopper, 1934).

Percent residual viable tumor (%RVT) will be summarized descriptively.

Combined efficacy based on both ORR per RECIST 1.1 and pCR and mPR per pathology review may be explored.

The distribution of EFS, DFS, and OS will be estimated using the Kaplan-Meier method. The median EFS, median DFS, and median OS along with 95% CIs will be presented and Kaplan-Meier estimates with 2-sided 95% CIs at specific time points will be summarized. The Kaplan Meier curves will be presented.

As regards the DFS endpoint, a descriptive summary will be performed for each subgroup of patients who receive adjuvant cemiplimab, adjuvant radiation therapy, and observation after surgery.

Change in planned surgery will be summarized descriptively. The proportion of patients for whom the surgical management plan (at time of screening) differed from the actual surgery after neoadjuvant therapy will be summarized both by investigator assessment and independent surgical expert committee.

Change in planned post-surgical management will be summarized descriptively. The proportion of patients for whom radiation therapy (or chemoradiation) was planned during screening but not actually administered after neoadjuvant cemiplimab and surgery will be summarized.

5.6.3. Analysis of Exploratory Efficacy Variables

Patterns of failure in patients with local, regional, or distant disease recurrence will be summarized descriptively.

Change in estimated costs due to change in surgical plan and change in estimated costs due to the change in post-surgical management plan will be summarized descriptively.

Health-related quality of life (HRQoL): the patient disposition and PRO completion rate at each assessment timepoint will be reported for the EORTC QLQ-C30. The change from baseline scores of each component of the EORTC QLQ-C30 will be summarized descriptively. The summary scores of each component of QLQ-C30 will also be graphically depicted by longitudinal plots. Additional analyses will be included in a separate PRO SAP.

5.6.4. Adjustment for Multiple Comparison

Adjustments to the significance level for the purposes of multiple testing are not applicable for this study.

5.7. Analysis of Safety Data

The analysis of safety and tolerability will be performed on the SAF, as defined in Section 3.2.

5.7.1. Adverse Events

Summaries that include frequencies and proportions of patients reporting AEs will include the PTs and the SOCs.

Summaries of all TEAEs will include: TEAEs, Treatment related TEAEs, Serious TEAEs, AESI, immune-related AEs (irAE), and IRR. For TEAEs, the following will be summarized:

- The number and proportions of patients reporting at least 1 TEAE, presented by SOC and PT
- TEAEs by severity, presented by SOC and PT

- TEAEs related to treatment, presented by SOC and PT
- TEAEs leading to permanent treatment discontinuation, presented by SOC, PT
- TEAEs leading to death, presented by SOC and PT
- IRRs by SOC, PT and NCI-CTCAE grade
- AESIs by SOC, PT and NCI-CTCAE grade
- Treatment-emergent irAEs by SOC, PT and NCI-CTCAE grade

For each TEAE summary presented by SOC and PT, the summary table will be sorted by decreasing frequency of SOC and PT. For TEAE summary presented by PT, the summary table will be sorted by decreasing frequency of PT.

Adverse events (AEs) during adjuvant cemiplimab will be summarized separately from AEs emerging in the neoadjuvant period. AEs will be collected from the date of first dose of adjuvant cemiplimab up to 90 days following the last dose.

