8.3.3. Immune-related Adverse Events and Study Drug Discontinuation

8.3.3.1. Identification of Immune-Related Adverse Events

Investigators must be extremely vigilant and be ready to intervene early in the management of irAEs, as the onset of symptoms of irAEs (eg, pneumonitis) may be subtle. An irAE can occur shortly after the first dose or several months after the last dose of treatment. All AEs of unknown

etiology associated with drug exposure should be evaluated to determine possible immune etiology. If an irAE is suspected, efforts should be made to rule out neoplastic, infectious, metabolic, toxin, or other etiologic causes prior to labeling an AE as an irAE.

Based on the emerging safety profile of cemiplimab and other antibodies targeting the PD-1/PD-L1 axis, working case definitions are provided in the Investigator's Brochure to help investigators distinguish irAEs from non-immune AEs commonly associated with PD-1 inhibition (Naidoo, 2015)(Weber, 2015). This is not exhaustive of all possible irAEs. Clinical presentations of less common irAEs, including neurologic, musculoskeletal, cardiac, renal, and ocular events (Hoffman, 2016)(Zimmer, 2016), should be reviewed in patients with concerning presentations.

The case definitions in the Investigator's Brochure have not been validated and are intended only as guidance for investigators to help distinguish irAEs from non-immune AEs. These definitions may evolve as clinical experience increases with cemiplimab and other antibodies targeting the PD-1/PD-L1 axis. Investigators' clinical judgment may include other factors when determining immune-relatedness.

Adverse events that meet the criteria for irAEs, as noted above in the Investigator's Brochure, should be reported as irAEs in the eCRF. If AEs corresponding to the common terms for irAEs are attributed as NOT related to cemiplimab by the investigator, additional information should be provided to substantiate an alternative attribution (eg, infectious diarrhea).

If not provided at the outset, this information may be requested by immediate edit checks or in subsequent queries. The sponsor may request additional information for any AE that is of a type known to be potentially immune-related (eg, rash, colitis, elevated transaminases, endocrine), but is deemed not an irAE by the investigator.

Any grade 3 or greater irAE should be reported as an adverse event of special interest (AESI) (Section 10.4.3).

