11.5.5.1. Adverse Events

Definitions

For safety variables, 3 observation periods are defined:

- The pretreatment period is defined as the time from signing the ICF to before the first dose of study drug.
- The treatment period is defined as the time from the day of first dose of neoadjuvant cemiplimab to the day of the last dose of neoadjuvant cemiplimab plus 90 days or to 1 day before patients receive their first dose of adjuvant cemiplimab or another anticancer systemic therapy, whichever is earlier.
- The post-treatment period is defined as the time starting one day after the end of on-treatment period.

Treatment-emergent AEs (TEAEs) are defined as AEs that developed or worsened during the on-treatment period and any treatment-related AEs that occur during the post-treatment period but prior to patients receiving their first dose of cemiplimab as adjuvant therapy or another anticancer systemic therapy.

Adverse events (AEs) during adjuvant cemiplimab will be summarized separately from AEs emerging in the neoadjuvant period. AEs will be collected from the date of first dose of adjuvant cemiplimab up to 90 days following the last dose. Additionally, any treatment-related AEs identified more than 90 days following the last dose will be captured.

Analysis

All AEs reported in this study will be coded using the currently available version of the Medical Dictionary for Regulatory Activities (MedDRA[®]). Coding will be to lowest level terms. The verbatim text, the preferred term, and the primary system organ class (SOC) will be listed.

Summaries of all TEAEs will include:

- The number (n) and percentage (%) of patients with at least 1 TEAE by SOC and preferred term
- TEAEs by severity (according to the grading scale outlined in Section 10.5.1), presented by SOC and preferred term

- TEAEs related to treatment, presented by SOC and preferred term
- Treatment-emergent AESIs (defined with a preferred term or a prespecified grouping)

Deaths and other SAEs will be listed and summarized.

Treatment-emergent adverse events leading to permanent treatment discontinuation will be listed and summarized.

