4.5. Safety Variables

Patient safety will be assessed through the collection of reported adverse events (AEs), clinical laboratory data, vital signs, ECG, and physical exam.

The observation period will be divided into three segments: pre-treatment, on-treatment and post-treatment.

- The pre-treatment period is defined as the time from signing the ICF to before the first dose of study drug.
- The treatment period is defined as the time from the day of first dose of neoadjuvant cemiplimab to the day of the last dose of neoadjuvant cemiplimab plus 90 days or to 1 day before patients receive their first dose of adjuvant cemiplimab or another anticancer systemic therapy, whichever is earlier.
- The post-treatment period is defined as the time starting one day after the end of on treatment period.

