4.5.1. Adverse Events and Serious Adverse Events

An AE is any untoward medical occurrence in a patient administered a study drug which may or may not have a causal relationship with the study drug. Therefore, an AE is any unfavorable and unintended sign (including abnormal laboratory finding), symptom, or disease which is temporally associated with the use of a study drug, whether or not considered related to the study drug.

An AE also includes any worsening (ie, any clinically significant change in frequency and/or intensity) of a pre-existing condition that is temporally associated with the use of the study drug.

The investigator (or designee) will seek information on AEs at each patient contact and record all AEs that occur from the time the informed consent is signed until 90 days after the last dose of study drug. Prior to initiation of study drug, only the following categories of AEs should be reported on the AE eCRF:

- SAEs
- Non-SAEs associated with a protocol-mandated intervention (eg, AEs related to an invasive procedure such as a biopsy)

Other AEs that occur prior to first treatment should be reported on the medical history eCRF.

All AEs after initiation of study drug and until 90 days after the last dose of study drug, regardless of relationship to study drug, will be reported on the AE eCRF. Additionally, any SAE or other AE of concern that the investigator believes may be related to study drug and that occurs later than 90 days after last study drug should be reported.

Pre-treatment AEs are defined as AEs that developed or worsened during the pre-treatment period.

Treatment-emergent AEs (TEAEs) are defined as AEs that developed or worsened during the on-treatment period and any treatment-related AEs that occur during the post-treatment period but prior to patients receiving their first dose of cemiplimab as adjuvant therapy or another anticancer systemic therapy.

Post-treatment AEs are defined as AEs that developed or worsened during the post-treatment period and are not considered drug related by the investigator.

All adverse events are to be coded using Medical Dictionary for Regulatory Activities (MedDRA).

The severity of AEs (including test findings classified as AEs) will be graded using the NCI-CTCAE v5. Adverse events not listed in the NCI-CTCAE v5 will be graded according to the following scale (Table 2):

Table 2: Grading System for Adverse Events Not Listed in NCI-CTCAE

Grade	Severity	Description

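### In patients given adjuvant cemiplimab, the SAP places a treatment-related adverse event more than 90 days after the last adjuvant dose in no safety summary

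*SAP*

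**What the plan says.** SAP 5.7.1 summarizes adverse events (AEs) during adjuvant cemiplimab separately from those of the neoadjuvant period and sets the window: "AEs will be collected from the date of first dose of adjuvant cemiplimab up to 90 days following the last dose". The paragraph ends there.

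Protocol 11.5.5.1, and the synopsis under its safety analysis methods, make the same two statements and add a third: "Additionally, any treatment-related AEs identified more than 90 days following the last dose will be captured". The same protocol section undertakes to list and summarize deaths and other serious AEs (SAEs), with no restriction to treatment-emergent events.

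Three SAP definitions decide where an event is counted:

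- **On-treatment period (SAP 4.5).** It starts at the first neoadjuvant dose and runs to 90 days after the last neoadjuvant dose, or "to 1 day before patients receive their first dose of adjuvant cemiplimab or another anticancer systemic therapy, whichever is earlier".
- **Treatment-emergent AE, TEAE (SAP 4.5.1).** Besides on-treatment events, it admits "any treatment-related AEs that occur during the post-treatment period but prior to patients receiving their first dose of cemiplimab as adjuvant therapy" or another systemic anticancer therapy.
- **Post-treatment AE (SAP 4.5.1).** "Post-treatment AEs are defined as AEs that developed or worsened during the post-treatment period and are not considered drug related by the investigator".

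On reporting, SAP 4.5.1 asks sites to report "any SAE or other AE of concern that the investigator believes may be related to study drug and that occurs later than 90 days" after the last study drug. SAP 1.2.4 lists two departures from the protocol's statistical section: the full analysis set definition and the removal of subgroup efficacy analysis.

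**The concern.** Protocol 8.3.3.1 warns about timing: "An irAE can occur shortly after the first dose or several months after the last dose of treatment". A drug-related event that appears some months after adjuvant treatment is therefore one the protocol expects and provides for. The SAP repeats the protocol's adjuvant paragraph without the sentence that covers such an event, and its other AE definitions were written around the neoadjuvant course.

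At stake is the related, serious and immune-related AE experience reported for patients who received both courses. The incidence of AEs, SAEs and deaths is a secondary endpoint (protocol 4.2), and protocol 3.2.3 says that Part 2 data could inform a future randomized trial. An analyst who applies the 90-day window as written would leave late related events out of the adjuvant tables, and a reader of the study report would not know.

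**Working it through.** The plan gives no figure to reproduce here. The check is a comparison of texts, followed by calendar arithmetic from the visit schedule.

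**Step 1. Compare the adjuvant paragraphs.** Protocol 11.5.5.1 has three elements: a separate summary, collection from first adjuvant dose to 90 days after the last, and capture of related events after that. SAP 5.7.1 has the first two only. SAP 1.2.4 does not mention the difference.

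**Step 2. Trace one event.** Take a patient who received adjuvant cemiplimab and has a related AE starting more than 90 days after the last adjuvant dose.

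- On-treatment? No. That period closes at the latest one day before the first adjuvant dose.
- TEAE? No. The late-related extension also closes at the first adjuvant dose.
- Post-treatment AE? No. By date the event lies in the post-treatment period, but the category takes only events that "are not considered drug related by the investigator".
- Adjuvant-period AE? No. The event is outside the 90-day window.

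Result: 0 of 4 categories.

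**Step 3. Look for a summary that does not depend on these categories.** SAP 5.7.1 introduces its related, serious, special-interest, immune-related, infusion-reaction and fatal-event summaries as summaries of TEAEs. None is stated to go beyond TEAEs, whereas the protocol's commitment on deaths and other SAEs has no such limit.

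**Step 4. Compare with a patient who had no adjuvant dose.** If that patient has started no other systemic anticancer therapy, the same late related event counts as a TEAE. The SAP therefore counts it after at most 4 doses (neoadjuvant only) and not after a course that may add up to 16 more.

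**Step 5. Place the follow-up visits against the cut-off.** Inputs: EOT2 is 21 to 37 days after the last adjuvant dose (protocol Table 3). The first follow-up visit is 4 months after EOT2 (footnotes to Table 4), with a window of ±30 days (Table 4). Follow-up lasts up to 3 years (protocol 6.1.4). One month is 365.25/12 = 30.44 days.

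- First follow-up visit: 21 + 4 × 30.44 = day 143, to 37 + 4 × 30.44 = day 159. Earliest with the window: 143 − 30 = day 113.
- End of follow-up: 21 + 36 × 30.44 = day 1117, to 37 + 36 × 30.44 = day 1133.
- Time beyond the cut-off: 1117 − 90 = 1027 days, to 1133 − 90 = 1043 days. As a share of time since the last dose, 1027/1117 and 1043/1133 are both about 92%.

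Every Table 4 visit, where AEs are under continuous monitoring, falls after day 90.

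**The case against.** The strongest reply is that nothing is lost. SAP 4.5.1 and protocol 10.4.1 both require late related SAEs and other AEs of concern to be reported, and the term study drug there is not confined to the neoadjuvant course. This stands. A reader might infer that the SAP discards these events, and the documents do not support that. The gap concerns where they are tabulated.

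A second reply is that the protocol says late related events will be captured, not summarized, and that its own TEAE definition also closes at the first adjuvant dose. This stands in part. Inclusion in the adjuvant table is the natural reading, because the sentence sits in the statistical section, in the paragraph that sets up that summary, but it is not stated outright. The undertaking on deaths and other SAEs is explicit, and the SAP's named summaries do not meet it for these events.

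A third reply is that the safety objective concerns neoadjuvant cemiplimab and that adjuvant treatment is optional. That limits the scope. It does not explain why a sentence covering patients who received both courses was left out without being declared.

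A reader might also take the 92% in step 5 as the share of events missed. It is a share of calendar time, and a maximum, because patients whose disease recurs move to survival follow-up only. Nor does the gap touch every event of special interest: infusion reactions are defined as occurring during the infusion or within 24 hours of its end (protocol 10.3.4), so of the two listed types only grade 3 or higher immune-related events can fall in it.

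**Conclusion.** The point holds as a gap in the analysis text that should be corrected. For patients who received adjuvant cemiplimab, the SAP names no summary that takes a related AE more than 90 days after the last adjuvant dose, and it departs from protocol 11.5.5.1 without saying so.

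The size in patients or events is unknown. The documents give neither the number expected to receive adjuvant cemiplimab nor a rate of late related events, so no undercount can be estimated. Late related AEs in patients with no adjuvant dose and no new systemic therapy are still counted as TEAEs. A late death still counts in overall survival; what is missing is its place in a safety table. The primary endpoint is not affected.

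The conclusion assumes that SAP 5.7.1 is applied as written. An analyst who fell back on the protocol might include the events, but the SAP gives no instruction to do so.

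**What to change.** Restore the protocol's sentence in SAP 5.7.1 and add what the protocol leaves implicit: treatment-related AEs more than 90 days after the last adjuvant dose are included in, or tabulated beside, the adjuvant AE summary, covering SAEs, grade 3 or higher immune-related AEs and deaths.

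Do not add a cut-off at the start of another anticancer therapy. The protocol's adjuvant sentence has none, and it would exclude some of the events at issue. If the distinction is wanted, flag the events that start after such therapy.

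A table footnote should say that the routine reporting rule beyond 90 days covers SAEs and AEs of concern, so non-serious late events may be incomplete.

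If the omission was deliberate, list it in SAP 1.2.4 with the reason.

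Cost: one SAP sentence and a small amount of extra tabulation, from events that the existing rule already requires sites to report.

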5.7.2. Clinical Laboratory Measurements

Laboratory test results will be summarized by baseline and change from baseline to each visit with descriptive statistics.

Summary tables for worst laboratory values during on-treatment period with NCI CTCAE all grade and grade ≥ 3 will be generated. Summary of Shift tables from baseline to worst post-treatment NCI CTCAE grade during on-treatment period will be generated.

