4.2. Secondary Endpoints

The secondary endpoints are:

- mPR rate assessed by independent central pathology review
- pCR rate and mPR rate assessed by local pathology review
- ORR prior to surgery, according to investigator assessment using RECIST 1.1
- Event free survival (EFS)
- Disease free survival (DFS)
- Overall survival (OS)
- Safety and tolerability as measured by the incidence of adverse events (AEs), serious adverse events (SAEs), deaths, and laboratory abnormalities
- Change in surgical plan in the screening period versus actual surgery after neoadjuvant cemiplimab
- Change in post-surgical management plan in the screening period versus actual post-surgical management

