5.7.5. Physical Exams

Number and proportion of patients with new or worsened physical exam abnormalities during on-treatment period will be summarized.

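### The only on-treatment window stops before adjuvant dosing, so no per-patient incidence of graded laboratory abnormalities or new exam findings is produced for adjuvant cemiplimab

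*SAP*

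**What the plan says.** SAP 4.5 sets up the safety time axis: "The observation period will be divided into three segments: pre-treatment, on-treatment and post-treatment". The on-treatment segment opens with the first neoadjuvant dose and has two possible ends. One is 90 days after neoadjuvant dosing stops. The alternative end is "1 day before patients receive their first dose of adjuvant cemiplimab or another anticancer systemic therapy, whichever is earlier". Everything from the following day onward is post-treatment. Protocol 11.5.5.1 has the same definition.

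Three outputs use that segment:

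- SAP 5.7.2, worst grade: "Summary tables for worst laboratory values during on-treatment period with NCI CTCAE all grade" and grade 3 or higher.
- SAP 5.7.2, shift tables from baseline to worst grade, with the same restriction. Protocol 11.5.5.2 restricts both laboratory outputs identically.
- SAP 5.7.5: "Number and proportion of patients with new or worsened physical exam abnormalities during on-treatment period will be summarized".

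Other adjuvant-phase data are provided for. SAP 5.7.1 states: "Adverse events (AEs) during adjuvant cemiplimab will be summarized separately from AEs emerging in the neoadjuvant period", with collection from the first adjuvant dose to 90 days after the last. SAP 5.5 summarizes exposure separately for the neoadjuvant and adjuvant periods. SAP 5.7.2 also summarizes laboratory change from baseline at each visit, without a period limit. Protocol 11.5.5.2 adds listings with out-of-range flags.

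The secondary endpoint in protocol 4.2 reads: "Safety and tolerability as measured by the incidence of adverse events (AEs), serious adverse events (SAEs), deaths, and laboratory abnormalities".

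**The concern.** A patient who takes adjuvant cemiplimab is back on study drug for up to 48 weeks, yet the SAP classes all of that time as post-treatment. For adverse events a separate summary covers this. For laboratory and exam data nothing equivalent exists, so the restriction in 5.7.2 and 5.7.5 removes the whole adjuvant phase from every table that counts patients with an abnormality.

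The data are collected. Protocol Table 3 schedules chemistry at each adjuvant dose and at EOT2, hematology every 6 weeks, and an examination at each dosing or evaluation visit. At stake is a simple descriptive result: how many adjuvant-treated patients reached grade 3 or higher on each laboratory test, and how many had a new or worsened exam finding. Protocol 3.2.3 says that Part 2 data could inform a later randomized adjuvant trial, and this is one of the figures its designers would look for.

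**Working it through.** **Exposure, reproduced from the schedule.** Part 1 doses fall on days 1, 22, 43 and 64, so 4 doses × 3 weeks = 12 weeks. Part 2 doses run every 3 weeks from week 0 to week 45, so 45/3 + 1 = 16 doses, and 16 × 3 = 48 weeks. Both agree with protocol 8.1 and SAP 2.3.

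**Share outside the window at full dosing.** Doses: 16/(4 + 16) = 80%. Weeks: 48/(12 + 48) = 80%. After 4 neoadjuvant doses, a patient who takes k adjuvant doses has k/(4 + k) outside: 20% for k = 1, 50% for k = 4, 80% for k = 16.

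**Can the window ever include an adjuvant dose?** Let L be the day of the last neoadjuvant dose and F the day of the first adjuvant dose. The period ends on min(L + 90, F − 1), or earlier if another systemic anticancer therapy starts. That is at most F − 1 on any schedule, so the answer is no by construction. With the protocol's visit windows (dose 4 on day 64 ± 3, surgery on day 75 to 100, EOT1 at 30 ± 10 days after surgery, first adjuvant dose at 21 ± 3 days after EOT1):

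| Schedule | L | F | L + 90 | F − 1 | Period ends |
|---|---|---|---|---|---|
| Earliest | 61 | 75 + 20 + 18 = 113 | 151 | 112 | 112 |
| Nominal | 64 | 85 + 30 + 21 = 136 | 154 | 135 | 135 |
| Latest | 67 | 100 + 40 + 24 = 164 | 157 | 163 | 157 |

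Over all 81 combinations of the early, nominal and late values, the period ends between days 112 and 157 and never contains an adjuvant dose. In 9 of the 81 the 90-day bound closes it even before the day preceding the first adjuvant dose.

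**Scheduled chemistry that falls outside.** Take a patient who completes both parts, with the day 1 pre-dose sample as baseline. Table 2 then gives 4 post-baseline draws (days 22, 43 and 64, and EOT1). Table 3 gives 17 (week 0, fifteen from week 3 to week 45, and EOT2), for a total of 4 + 17 = 21. The 15 + 1 = 16 draws after the first adjuvant dose all lie outside. A week 0 sample drawn on the dosing day makes it 17.

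**What each remaining route shows for adjuvant dosing.**

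| Output | Covers adjuvant dosing? | Counts patients by worst grade or new finding? |
|---|---|---|
| Laboratory worst-grade and shift tables (SAP 5.7.2) | No | Yes |
| Exam abnormalities (SAP 5.7.5) | No | Yes (number and proportion) |
| By-visit laboratory change (SAP 5.7.2) | Yes | No |
| Flagged listings (protocol 11.5.5.2) | Yes | No |
| Adjuvant AE summary (SAP 5.7.1) | Yes | Only abnormalities recorded as AEs |

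SAP 6.4 lets unscheduled values count toward worst post-baseline values, but that settles which assessments qualify, not which period. It also keeps extra values, including those drawn while managing an adverse event, out of the by-visit summaries. The ECG shift tables in SAP 5.7.4 have the same limit without consequence, since Table 3 schedules no ECG.

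**Effect of a second window.** On the nominal schedule the last adjuvant dose is on day 136 + 15 × 21 = 451. A window from the first adjuvant dose to the last + 90 days covers days 136 to 541, which is 406 days. The outputs would then span up to 20 of 20 doses instead of at most 4 of 20.

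**The case against.** The strongest reply is scope. Protocol 2.2 and SAP 1.2.2 word the safety objective for neoadjuvant cemiplimab, and both documents say that the primary objective is neoadjuvant and not adjuvant therapy. Protocol and SAP use the same window, which suggests a choice. This stands, and it lowers the severity. It does not explain why AEs and exposure are reported for adjuvant treatment while laboratory and exam incidence is not, and the endpoint in protocol 4.2 carries no Part 1 restriction.

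The second reply is that actionable events are captured elsewhere, and this largely stands too. A reader might infer that adjuvant laboratory data go unreported, or that an immune-related hepatitis or nephritis first seen in Part 2 would be missed. The documents do not support that. Protocol 10.4.5 makes an abnormal result an AE when, for example, it requires further diagnostic testing, intervention or significant added therapy. Appendix 2 attaches drug-withholding and corticosteroid guidance to ALT/AST above 3 to 10 × ULN and to creatinine above 2 to 3 × baseline, so such cases would ordinarily qualify. Grade 3 or higher immune-related AEs are also reportable within 24 hours (protocol 10.4.3). What can escape is a graded value that triggers nothing. Protocol Table 1 calls for no hold for most grade 1 to 3 hematological toxicity, and 10.4.5 says that repeating a test does not by itself make an AE.

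A reader might also make something of the SAP 4.5.1 wording: "Post-treatment AEs are defined as AEs that developed or worsened during the post-treatment period and are not considered drug related by the investigator". Read literally, this covers unrelated AEs during adjuvant dosing. The label feeds no table listed in SAP 5.7.1, and those events fall in the adjuvant AE summary in any case, so nothing in the analysis turns on it.

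**Conclusion.** The gap is real and follows directly from the definitions. As written, no table gives the number of patients by worst laboratory grade, by grade shift, or with new or worsened exam findings during adjuvant cemiplimab. Individual values stay visible and actionable ones should appear as AEs, so the loss is mainly the worst-grade incidence, especially for graded values that led to no action.

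Its size depends on two things that the documents do not give: how many patients choose adjuvant cemiplimab (anywhere from 0 to all of about 76, with radiation and observation as alternatives) and how many doses they complete. The figure of 16 of 20 doses is for full dosing in a patient who takes the option, not an average. No efficacy result, primary analysis or AE summary is affected. With the safety objective worded for neoadjuvant treatment, severity is minor to moderate: a cheap improvement.

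**What to change.** In SAP 4.5, add an adjuvant on-treatment period from the first adjuvant dose to the earlier of the last adjuvant dose + 90 days and the day before another systemic anticancer therapy. The 90 days match the adjuvant AE window in SAP 5.7.1. Repeat the 5.7.2 worst-grade and shift tables and the 5.7.5 count for adjuvant-treated patients over that period. State one baseline, for example the last value before the first adjuvant dose, because the general rule in SAP 6.1 does not say which administration of study drug applies here.

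The 90-day tail adds few scheduled laboratory values. EOT2 falls 21 to 37 days after the last dose, and the next visit is 4 months ± 30 days later, so no earlier than about 21 + 120 − 30 = 111 days after the last dose. The tail is there for consistency with the AE window and for unscheduled values.

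The cost is a paragraph of SAP text and a second run of existing table programs on data already collected. The downside is a few extra tables.
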